### 11.1 Antitumor Effect – CNS disease

Tumor response and progression for CNS disease will be assessed centrally by the DF/HCC Tumor Imaging Metrics Core according to RANO-BM criteria and according to iRANO criteria. Please refer to the full publications for additional details.

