#### 11.1.1.5 Evaluation of Non-Target Lesions

Non-target lesions should be assessed qualitatively at each of the time points specified in the protocol.

- **CR:** Requires all of the following: disappearance of all enhancing CNS non-target lesions, no new CNS lesions.
- **Non-CR/Non-PD:** Persistence of one or more non-target CNS lesion(s).
- **PD:** Any of the following: unequivocal progression of existing enhancing non-target CNS lesions, new lesion(s) (except while on immunotherapy-based treatment), or unequivocal progression of existing tumor-related non-enhancing (T2/FLAIR) CNS lesions. In the case of immunotherapy-based treatment, new lesions alone may not constitute progressive disease (see “Guidance in the case of new lesion(s) while on immunotherapy” below).

Special Notes on the Assessment of Target and Non-Target CNS Lesions:

- a) *Target lesions that become too small to measure:* While on study, all CNS target lesions should have their actual measurement recorded, even when very small (e.g., 2 mm). If the lesion disappears, the value should be recorded as 0 mm. However, if the

- lesion is sufficiently small (but still present) that the radiologist does not feel comfortable assigning an exact measure, a default value of 5 mm should be recorded on the case report form.
- b) *Lesions that coalesce on treatment:* As lesions coalesce, a plane between them may be maintained that would aid in obtaining maximum LD of each individual lesion. If the lesions have truly coalesced such that they are no longer separable, the vector of the longest diameter in this instance should be the maximum LD for the ‘coalesced’ lesion.

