  - c) *Definition of new lesion(s):* The finding of a new CNS lesion should be unequivocal and not due to technique or slice variation. A new lesion is one that was not present on prior scans. If the MRI is obtained with  $\leq 1.5$  mm slice thickness, then the new lesion should also be visible in axial, coronal, and sagittal reconstructions of  $\leq 1.5$  mm projections. If a new lesion is equivocal, for example because of its small size (i.e.,  $\leq 5$  mm), continued therapy may be considered, and follow up evaluation will clarify if it represents truly new disease. If repeat scans confirm there is definitely a new lesion, then progression should be declared using the date of the initial scan showing the new lesion. In the case of immunotherapy, new lesions alone may not constitute progressive disease (see “Guidance in the case of new lesion(s) while on immunotherapy” below).
  - d) *Definition of Unequivocal Progression of Non-Target Lesion(s):* When the patient also has measurable disease, to achieve ‘unequivocal progression’ on the basis of non-target disease alone, there must be an overall level of substantial worsening in non-target disease such that, even in the presence of SD or PR in target disease, the overall tumor burden has increased sufficiently to merit discontinuation of therapy. When the patient has only non-measurable disease, there must be an overall level of substantial worsening to merit discontinuation of therapy.

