  - e) *Guidance in the Case of Uncertain Attribution of Radiographic Findings and/or Equivocal Cases:* The RANO-BM group acknowledges that in the case of patients followed after SRS or during immunotherapy-based approaches, there may be radiographic evidence of enlargement of target and non-target lesions which may not necessarily represent tumor progression. If there is evidence of radiographic progression but there is clinical evidence supporting the possibility that the radiological changes are due to treatment effect (and not to progression of cancer), additional evidence is required to distinguish true progression versus treatment effect as standard MRI alone is not sufficient. The methods used to distinguish between the two entities should be specified prospectively in the clinical protocol. one or more of the following options: (1) Repeat the scan at the next protocol scheduled evaluation or sooner, and generally within ~6 weeks. An investigator may choose a shorter time interval in the case of progressive symptoms or other clinically concerning findings. If there is continued increase in enhancement concerning for tumor growth, then this may be consistent with radiographic progression and the patient should be taken off study (Figure 2 in the original publication). If the lesion is stable or decreased in size, then this may be consistent with treatment effect and the patient may remain on study (Figure 3 in the original publication). For patients with equivocal results even on the next restaging scan, the scan may be repeated again at a subsequent protocol scheduled evaluation or sooner although surgery and/or use of an advanced imaging

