modality (in the case of SRS/SRT) are strongly encouraged. (2) Surgical pathology obtained via biopsy or resection. (3) For SRS/SRT treated lesions, an advanced imaging modality such as perfusion MR imaging, MR spectroscopy, or FLT or FDG positron emission tomography (PET) may be used as additional evidence of tumor progression or treatment effect/radionecrosis. Upon review of the literature and extensive discussions by the Working Group, we were not able to conclude that any one modality or approach can be recommended across all patients to distinguish between radiation necrosis versus true progression, as the literature is not sufficiently robust, and recommend clinical judgment and involvement of a multidisciplinary team. We recognize this is less than satisfactory and agree that developing more sensitive and specific methods for distinguishing between treatment effect and tumor progression are needed. We should also note that these advanced imaging modalities have not been extensively studied with regards to immunotherapy-based approaches and therefore are cannot be recommended for distinguishing tumor progression versus immune-related changes at this time. Regardless of the additional testing obtained, if subsequent testing demonstrates that progression has occurred, the date of progression should be recorded as the date of the scan at which this issue was first raised. Patients may also have an equivocal finding on a scan (for example, a small lesion that is not clearly new). It is permissible to continue treatment until the next protocol scheduled evaluation. If the subsequent evaluation demonstrates that progression has indeed occurred, the date of progression should be recorded as the date of the initial scan where progression was suspected.

Notes Regarding Corticosteroid Use and Clinical Deterioration:

- a) An increase in corticosteroid dose alone, in the absence of clinical deterioration related to tumor, will not be used as a sole determinant of progression. Patients with stable imaging studies whose corticosteroid dose was increased for reasons other than clinical deterioration related to tumor do not qualify for stable disease or progression. They should be observed closely. If their corticosteroid dose can be reduced back to baseline, they will be considered as having stable disease; if further clinical deterioration related to tumor becomes apparent, they will be considered to have progression.

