**Table 1**

Summary of the Proposed RANO Response Criteria for CNS Metastases

Criterion	CR	PR	SD	PD
Target lesions	None	≥ 30% decrease in sum LD relative to baseline	< 30% decrease relative to baseline but < 20% increase in sum LD relative to nadir	≥ 20% increase in sum LD relative to nadir*
Non-target lesions	None	Stable or improved	Stable or improved	Unequivocal PD*
New lesion(s)**	None	None	None	Present*
Corticosteroids	None	Stable or decreased	Stable or decreased	NA †
Clinical status	Stable or improved	Stable or improved	Stable or improved	Worse*
Requirement for response	All	All	All	Any †

Abbreviations: CNS = central nervous system; CR = complete response; LD= longest dimension; NA = not applicable; PD = progressive disease; PR= partial response; RANO= Response Assessment in Neuro-Oncology; SD = stable disease.

\*Progression occurs when this criterion is met.

\*\*New lesion = new lesion not present on prior scans and visible in at least 2 projections. If a new lesion is equivocal, for example because of its small size, continued therapy may be considered, and follow up evaluation will clarify if it represents truly new disease. If repeat scans confirm there is definitely a new lesion, then progression should be declared using the date of the initial scan showing the new lesion. For immunotherapy based approaches, new lesions alone to do not define progression (See “Guidance in the Case of New Lesion(s) while on Immunotherapy”).

†Increase in corticosteroids alone will not be taken into account in determining progression in the absence of persistent clinical deterioration.

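### Section 11.1 is inconsistent on whether an isolated, unequivocal new brain lesion on atezolizumab is a primary PFS event, and the guidance it cites is not in the document

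*Combined protocol and SAP*

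**What the plan says.** Sections 13.1 and 13.5 define the primary event as the first detected radiologic progression in either compartment, or death. For the intracranial part both point to RANO-BM as set out in Section 11.1.

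On new CNS lesions, Section 11.1 makes these statements:

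- Section 11.1.1.5, non-target PD, includes "new lesion(s) (except while on immunotherapy-based treatment").
- The next sentence is weaker: "In the case of immunotherapy-based treatment, new lesions alone may not constitute progressive disease".
- Note c of the same section is also weak: "In the case of immunotherapy, new lesions alone may not constitute progressive disease".
- Table 1 (RANO criteria for CNS metastases) lists a new lesion under PD, but its double-asterisk footnote says: "For immunotherapy based approaches, new lesions alone to do not define progression".

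Section 11.1.1.5 (both places) and the Table 1 footnote send the reader to a titled item of guidance on new lesions during immunotherapy. No such item appears.

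Elsewhere, Section 5.5 says the primary endpoint uses standard RANO-BM for the CNS, with the immune criteria governing how long a patient may stay on therapy. Section 13.7 lists RANO-BM PFS, where the first progression counts as the event, separately from iRANO PFS. Objective 1.4.10 names new lesions among the types of CNS progression.

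**The concern.** A reader who follows the exclusion and a reader who follows Section 5.5 would classify the same scan differently for the primary endpoint. This is not a rare corner of the protocol. Every participant starts atezolizumab on day 1 of cycle 1, which is also time zero for PFS, so the exception could apply to any new brain lesion seen on treatment.

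The trial has one arm and tests a median against a fixed 2 months (Section 13.2). A definition that leaves out events counted by the null's sources lengthens PFS without any treatment effect. Section 13.2 does not say how those sources handled new lesions.

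The documents do not give the share of first events that would be isolated new CNS lesions. Section 13.7 expects irradiated lesions to respond well, and Section 13.2 cites intracranial progression at 2.5 months after stereotactic radiation in triple-negative disease. The share therefore need not be small, but that is an inference.

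**Working it through.** **1. The text.**

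| Place | Isolated new CNS lesion on immunotherapy |
|---|---|
| 11.1.1.5, PD bullet | Not PD |
| 11.1 Table 1, footnote | Not PD |
| 11.1.1.5, next sentence, and note c | May not be PD; see guidance (absent) |
| 5.5 | Primary endpoint by standard RANO-BM; immune criteria are for continuation |
| 13.7 | RANO-BM PFS: first progression is the event; iRANO PFS is separate |
| 1.4.10 | New lesions are a type of CNS progression |

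Note e of 11.1.1.5 does not fill the gap. It deals with cases where "there may be radiographic evidence of enlargement of target and non-target lesions which may not necessarily represent tumor progression", and with equivocal scans: "Patients may also have an equivocal finding on a scan (for example, a small lesion that is not clearly new"). Neither is an unequivocal new lesion. Section 11.1 runs unbroken from its opening to Table 1, so the absent guidance is not explained by removed pages.

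**2. The plan's own figure.** Inputs from Sections 13.2 and 13.5: n = 45, medians 2 and 3.5 months, one-sided alpha 0.05, a Brookmeyer-Crowley type test and Greenwood variance. With at least 6 months of follow-up and assuming no early drop-out, nobody is censored before month 2. The test is then of S(2) = 0.5 with X of 45 event-free.

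- Plain scale: z = (s - 0.5) / sqrt(s(1 - s)/45). X = 27 gives 1.369, X = 28 gives 1.691; reject at 28 or more (critical value 1.645).
- Log-log scale: X = 28 gives 1.548, X = 29 gives 1.809; reject at 29 or more.
- Under the alternative with exponential times, S(2) = 0.5^(2/3.5) = 0.673. P(X >= 28) = 81.3% and P(X >= 29) = 71.8%. The stated 80% is reproduced on the plain scale.
- Under the null, P(X >= 29) = 3.6% and P(X >= 28) = 6.8%. This is the 4-7% baseline.

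**3. Effect of never counting isolated new lesions.** Assumptions: they are a fraction f of first events (proportional cause-specific hazards); the null's sources counted them; and the recorded 2-month event-free rate is 50% when they are counted. Per Section 10 note g, the first two scans fall in days 15-21 of cycles 2 and 4, that is days 36-42 and 78-84. Month 2 (day 61) lies between them. If all events are found at scans, leaving out the fraction f gives S(2) = 0.5^(1-f).

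| f | S(2) | Expected event-free of 45 | P(X >= 29) to P(X >= 28) |
|---|---|---|---|
| 0 | 0.500 | 22.5 | 3.6-6.8% |
| 10% | 0.536 | 24.1 | 9.4-15.6% |
| 20% | 0.574 | 25.8 | 21.3-31.1% |
| 30% | 0.616 | 27.7 | 40.8-52.9% |

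**4. Sensitivity.** Let a share q of events be deaths or other events off the scan schedule, with the first scan on day 42. The exponent becomes [(1 - q - f) x 42 + q x 61] / [(1 - q) x 42 + q x 61]. For q = 10% and f = 10% this is 39.7/43.9 = 0.904, so S(2) = 0.534. For q from 10 to 30%, the rejection probability spans 8.5-15.1%, about 18-30% and 33-50% at f = 10, 20 and 30%.

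**5. Size in months.** In continuous time, a 2-month median with these lesions counted becomes 2/(1 - f) = 2.22, 2.50 or 2.86 months without them. The difference is about 0.2, 0.5 or 0.9 month, against a target effect of 3.5 - 2 = 1.5 months.

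**The case against.** **The date is already settled.** This stands. A reader might infer that the plan also fails to say from which date a new lesion would count. The documents do not support that. Note c and the Table 1 footnote date a lesion confirmed as new to the scan that first showed it. Note e says of suspected progression later shown that "the date of progression should be recorded as the date of the initial scan where progression was suspected". Sections 11.4.2 and 13.7 back-date as well, and Sections 13.1 and 13.5 use first detection. It remains only to say that the same date applies here. A scenario in which such lesions are dated to the following scan has no basis in the text.

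**Confirmation is partly covered.** Section 10 note g allows 4-6 weeks on study to confirm CNS PD on MRI. That gives an interval, but does not decide whether a new lesion alone is PD.

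**Sections 5.5, 13.7 and 1.4.10 already show that it counts.** They point that way, and the fix follows them. They do not cancel an explicit exclusion in the section that the endpoint cites.

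**The publications supply the rule.** Section 11.1 says "Please refer to the full publications for additional details" and assigns reading to one central imaging core. The missing guidance may be in a publication, which cannot be checked here. The pointer does not say which of the protocol's differing statements governs.

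**Table 1 contradicts itself.** A reader might say so, but it is a rule with a footnoted exception. The inconsistency is between that exception, the weaker wording and the sections outside 11.1.

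**The numbers rest on assumptions.** They do: both f and the null's definition are assumed. The gap in the definition needs neither.

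**Conclusion.** The inconsistency is real and affects the primary endpoint: the documents do not settle whether an isolated, unequivocal new CNS lesion on atezolizumab is a PFS event. It should be resolved before the primary analysis, because a choice made after the data are seen could be driven by the result.

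The consequence is conditional. If such lesions are never counted, if they make up 10, 20 or 30% of first events, and if the sources of the 2-month null counted them, the chance of rejecting a true null is about 9-16%, 21-31% or 41-53% instead of 4-7%. If they are counted, there is no inflation from this cause. It would be wrong to infer that the trial's type I error is inflated as planned, because the documents give neither the share nor the null's definition, and the exclusion is only one of the readings they allow.

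**What to change.** Reconcile Section 11.1.1.5 (the PD bullet, the sentence after it, and note c) and the Table 1 footnote with Sections 5.5, 13.1, 13.5 and 13.7. For the primary PFS, state that an unequivocal new CNS lesion counts as progression and is dated to the first scan showing it. Keep the immunotherapy exception for the exploratory iRANO PFS. Report PFS under the exception as a sensitivity analysis from the same scans. State how the sources of the 2-month null treated new lesions.

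If the sponsor prefers to keep the exception in the primary endpoint, the cited guidance must be written into the protocol and the 2-month null re-justified under it.

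The cost is an amendment to wording; no new scans, patients or readers are needed. The downside is that observed PFS may be shorter than under the exception, by about 0.2, 0.5 or 0.9 month in the median at the assumed shares, so the null is less likely to be rejected.

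Separately, Section 1.1.1 ends treatment at progression by RANO-BM and RECIST, while Section 5.5 lets it continue until progression by iRANO and/or irRC. These passages must be reconciled, so that a change to the endpoint wording does not alter treatment continuation by accident. No treatment rule is proposed here.

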**Table 1**

Summary of the Proposed RANO Response Criteria for CNS Metastases

Criterion	CR	PR	SD	PD
Target lesions	None	≥ 30% decrease in sum LD relative to baseline	< 30% decrease relative to baseline but < 20% increase in sum LD relative to nadir	≥ 20% increase in sum LD relative to nadir*
Non-target lesions	None	Stable or improved	Stable or improved	Unequivocal PD*
New lesion(s)**	None	None	None	Present*
Corticosteroids	None	Stable or decreased	Stable or decreased	NA †
Clinical status	Stable or improved	Stable or improved	Stable or improved	Worse*
Requirement for response	All	All	All	Any †

Abbreviations: CNS = central nervous system; CR = complete response; LD= longest dimension; NA = not applicable; PD = progressive disease; PR= partial response; RANO= Response Assessment in Neuro-Oncology; SD = stable disease.

\*Progression occurs when this criterion is met.

\*\*New lesion = new lesion not present on prior scans and visible in at least 2 projections. If a new lesion is equivocal, for example because of its small size, continued therapy may be considered, and follow up evaluation will clarify if it represents truly new disease. If repeat scans confirm there is definitely a new lesion, then progression should be declared using the date of the initial scan showing the new lesion. For immunotherapy based approaches, new lesions alone to do not define progression (See “Guidance in the Case of New Lesion(s) while on Immunotherapy”).

†Increase in corticosteroids alone will not be taken into account in determining progression in the absence of persistent clinical deterioration.

## 11.2 Antitumor Effect – non-CNS disease

Response and progression in extracranial sites of metastases will be evaluated in this study using the international criteria proposed by the RECIST 1.1 criteria [Eisenhauer *et al.*, 2009]. Changes in the largest diameter (unidimensional measurement) of the tumor lesions and the shortest diameter in the case of malignant lymph nodes are used in the RECIST criteria.

### 11.2.1 RECIST 1.1 Definitions

Evaluable for Target Disease response. Only those participants who have measurable disease outside the field of radiation present at baseline, have received at least one cycle of therapy, and have had their disease re-evaluated will be considered evaluable for target disease response. These participants will have their response classified according to the definitions stated below. (Note: Participants who exhibit objective disease progression prior to the end of cycle 1 will also be considered evaluable.)

Evaluable Non-Target Disease Response. Participants who have lesions present at baseline that are evaluable but do not meet the definitions of measurable disease, have received at least one cycle of therapy, and have had their disease re-evaluated will be considered evaluable for non-target disease. The response assessment is based on the presence, absence, or unequivocal progression of the lesions.

### 11.2.2 Disease Parameters

Measurable disease. Measurable lesions are defined as those that can be accurately measured in at least one dimension (longest diameter to be recorded) as  $\geq 20$  mm by chest x-ray or  $\geq 10$  mm with CT scan, MRI, or calipers by clinical exam. All tumor measurements must be recorded in millimeters (or decimal fractions of centimeters).

Note: Tumor lesions that are situated in a previously irradiated area are not considered measurable.

Malignant lymph nodes. To be considered pathologically enlarged and measurable, a lymph node must be  $\geq 15$  mm in short axis when assessed by CT scan (CT scan slice thickness recommended to be no greater than 5 mm). At baseline and in follow-up, only the short axis will be measured and followed.

Non-measurable disease. All other lesions (or sites of disease), including small lesions (longest diameter  $< 10$  mm or pathological lymph nodes with  $\geq 10$  to  $< 15$  mm short axis), are considered non-measurable disease. Bone lesions, leptomeningeal disease, ascites, pleural/pericardial effusions, lymphangitis cutis/pulmonitis, inflammatory breast disease, abdominal masses (not followed by CT or MRI), and cystic lesions are all considered non-measurable.

Note: Cystic lesions that meet the criteria for radiographically defined simple cysts should not be considered as malignant lesions (neither measurable nor non-measurable)

since they are, by definition, simple cysts.

‘Cystic lesions’ thought to represent cystic metastases can be considered as measurable lesions, if they meet the definition of measurability described above. However, if non-cystic lesions are present in the same participant, these are preferred for selection as target lesions.

Target lesions. All measurable lesions up to a maximum of 2 lesions per organ and 5 lesions in total, representative of all involved organs, should be identified as **target lesions** and recorded and measured at baseline. Target lesions should be selected on the basis of their size (lesions with the longest diameter), be representative of all involved organs, but in addition should be those that lend themselves to reproducible repeated measurements. It may be the case that, on occasion, the largest lesion does not lend itself to reproducible measurement in which circumstance the next largest lesion which can be measured reproducibly should be selected. A sum of the diameters (longest for non-nodal lesions, short axis for nodal lesions) for all target lesions will be calculated and reported as the baseline sum diameters. If lymph nodes are to be included in the sum, then only the short axis is added into the sum. The baseline sum diameters will be used as reference to further characterize any objective tumor regression in the measurable dimension of the disease.

Non-target lesions. All other lesions (or sites of disease) including any measurable lesions over and above the 5 target lesions should be identified as **non-target lesions** and should also be recorded at baseline. Measurements of these lesions are not required, but the presence, absence, or in rare cases unequivocal progression of each should be noted throughout follow up.

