## 9.2 Fresh Tissue Collection

### 9.2.1 Collection

Biopsies are required at baseline (pre-treatment) and C2D1 (performed as close to C2D1 as possible but between C2D1 and C2D21). An optional biopsy may be collected at the time of progression for patients who achieved an objective response and/or a prolonged stable disease ( $\geq 24$  weeks). The biopsies may be waived on the first 6 participants enrolled to the safety run in phase.

Biopsies should not be performed on Friday afternoons, as there may not be time for processing of the fresh tissue. If a biopsy must be performed on Friday morning, the lab of [REDACTED] must be notified ahead of time to ensure that there will be adequate time for processing fresh tissue, since fresh tissue cannot be stored over the weekend [REDACTED]

[REDACTED] The specimens in RNALater and formalin may be stored over the weekend and shipped on Monday. Specimens in RNA Later and formalin should be stored at room temperature until shipment.

Ideally, five core biopsies will be obtained:

- Two cores should be placed in 10% neutral buffered formalin tube supplied by the study.
- One cores should be placed in RNAlater
- Two cores should be placed in sterile DMEM

The order of specimen collection should be:

- First core: 10% neutral buffered formalin
- Second core: Sterile DMEM
- Third core: RNAlater
- Fourth core: Sterile DMEM
- Fifth core: 10% neutral buffered formalin

If additional cores are obtained, they should be processed as follows:

- Sixth core: RNAlater
- Seventh core: 10% neutral buffered formalin

Guidelines for biopsy from various metastatic sites can be found in Appendix C.

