### 11.4.3 Definition of Abscopal response

As described previously, abscopal response is defined as a decrease in the longest diameter of at least 30% in any measurable ( $\geq 1$  cm) non-irradiated lesion from baseline [Golden *et al.*, 2015]. In patients with more than three lesions, the non-irradiated lesions will be measured individually for response to treatment. The best abscopal responding lesion will be reported.

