## 13.6 Analysis of Key Secondary Endpoints

### 13.6.1 Extracranial Objective Response:

The design of this study, which involves radiation to CNS metastases in the setting of evaluable extracranial disease, provides a unique opportunity to test whether there is a signal consistent with an abscopal effect with the addition of stereotactic radiation to atezolizumab. Extracranial response will be assessed according to RECIST 1.1, and will be evaluated as a key secondary objective using a one-sample exact binomial test (one-sided type I error  $\leq 0.05$ ).

In prior studies evaluating immune checkpoint inhibitors in metastatic triple negative breast cancer (which excluded patients with active CNS metastases), the extracranial response rate has ranged from 8.6% in an unselected population [Dirix *et al.*, 2015] (Dirix *et al.*, 2015), to 18-19% in patients selected for tumor PD-L1 expression [Emens *et al.*, 2015, Nanda *et al.*, 2016]. Based on these prior studies of single agent PD1/PDL1 blockade in unselected triple negative breast cancer, the null hypothesis is that the extra-CNS response rate is 10% or lower.

With a sample size of 45 defined by the primary endpoint of PFS, there will be 82% power to reject the null hypothesis if the true extra-CNS response rate is 25% with stereotactic radiation given in combination with atezolizumab.

The observed extra-CNS response rate will be reported with a two-sided 90% confidence level which given the sample size will have a maximum width of 26%. In addition, we intend to evaluate extracranial objective according abscopal response as by Golden *et al.* [Golden *et al.*, 2015].

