## APPENDIX H GUIDELINES FOR COLLECTING RESEARCH BIOPSY TISSUE

Tissue specimens will be collected from metastatic lesions using standard institutional procedures. The amount of tissue collected may follow the guidelines listed below:

*Skin/chest wall:* Because the yield of malignant tissue from skin/chest wall biopsies tends to be relatively low, if a patient has another accessible site of disease (i.e. lymph node, liver), that site should be biopsied preferentially. If skin/chest wall is the only biopsy-accessible site, then a goal of 2 5-mm punch biopsies will be obtained.

*Lymph node:* A goal of 5-7 core biopsy specimens will be obtained using an 18-gauge needle.

*Liver:* A goal of 5-7 core biopsy specimens will be obtained using an 18-gauge needle.

*Lung:* Because of the risk of pneumothorax associated with core needle biopsies of lung nodules, no core biopsies of lung nodules are mandated on this protocol, unless they are clinically indicated.

*Bone:* Because the yield of malignant tissue from bone biopsies tends to be relatively low, if a patient has another accessible site of disease (i.e. lymph node, liver), that site should be biopsied preferentially. If bone is the only biopsy-accessible site, then a goal of 5-7 core biopsy specimens will be obtained using an 11-13 gauge needle.

**Please note that the above are guidelines for the amount of tissue to be obtained, and are not meant to replace clinical judgment at the time the procedure is performed.** Less than the goal quantity of tissue is accepted for each type of biopsy, and will be left to the clinical judgment of the physician performing the procedure.

Coded laboratory specimens will be stored in the Tumor Bank of the DFCI. These specimens will become the property of DFCI. Patients will be informed that their specimens may be used for research by investigators at DF/HCC and other approved collaborators. Shared specimens will be identified with a sample ID number; all patient identifying material will be removed.

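### No rule separates the lesions sampled for research biopsies from those measured for extracranial and abscopal response, so a biopsy effect could enter the response data

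*Combined protocol and SAP*

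**What the plan says.** **Target lesions (Section 11.2.2).** All measurable lesions become targets, up to two per organ and five in total. On choice, "Target lesions should be selected on the basis of their size (lesions with the longest diameter), be representative of all involved organs". The sentence goes on to ask for lesions that can be measured reproducibly, and the next largest lesion is taken where the largest cannot. Biopsy is not mentioned.

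**Abscopal response (Section 11.4.3, Definition of Abscopal response).** Any measurable non-irradiated lesion of at least 1 cm qualifies with a 30% fall in longest diameter, and "The best abscopal responding lesion will be reported".

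**Biopsies.** Section 9.2.1: "Biopsies are required at baseline (pre-treatment) and C2D1 (performed as close to C2D1 as possible but between C2D1 and C2D21"). The study calendar limits the requirement to patients with accessible disease outside the radiation field. The biopsies may be waived for the first six participants (Sections 3.1.7 and 9.2.1). Appendix H aims for 5-7 18-gauge cores from node or liver. For skin, "If skin/chest wall is the only biopsy-accessible site, then a goal of 2 5-mm punch biopsies will be obtained".

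**Timing.** The baseline biopsy and the baseline scan each fall within four weeks before the first dose, and no order is stated. The cycle 2 biopsy window (days 1-21) overlaps the first restaging window (days 15-21 of cycle 2).

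**Test (Section 13.6.1).** Under the null, "the null hypothesis is that the extra-CNS response rate is 10% or lower". The rate is tested with an exact one-sample binomial test at one-sided 0.05, and "With a sample size of 45 defined by the primary endpoint of PFS, there will be 82% power to reject the null hypothesis" at a true rate of 25%.

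**The concern.** The accessible extracranial lesions that can be sampled are drawn from the same pool that supplies the RECIST targets and the abscopal lesion. In a patient with few measurable lesions, the Section 11.2.2 rule makes the sampled lesion a target. Appendix H strengthens the overlap: it prefers sites such as node and liver to skin and bone, and it does not mandate lung cores. Bone lesions are non-measurable anyway.

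A biopsy can shrink a lesion by removing tissue or by scarring, or enlarge it by swelling or bleeding. Three endpoints are exposed:

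- extracranial ORR, a key secondary endpoint with a formal test;
- the exploratory abscopal rate, where reporting the best lesion favours upward error;
- PFS, because progression is judged against the smallest sum on study, and a nadir lowered by biopsy can bring progression forward.

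The trial has one arm, so no comparator absorbs the artefact. The four-week confirmation in the RECIST table is footnoted as applying only where response is the primary endpoint. Here that endpoint is PFS, so confirmation does not clearly protect ORR.

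**Working it through.** **1. Is there a separating rule?** The places where one could stand are Section 9 (opening text), Section 9.2.1, the study calendar notes, Section 11.2.2, Section 11.4.3 and Appendix H. None says that the sampled lesion must be non-target, must differ from the abscopal lesion, or must be imaged before sampling.

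**2. The plan's own ORR figure.** Inputs from Section 13.6.1: n = 45, null 10%, alternative 25%, one-sided exact binomial test at 0.05.

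- P(X ≥ 8 | 45, 0.10) = 0.0757, above 0.05.
- P(X ≥ 9 | 45, 0.10) = 0.0320, so the cutoff is 9 of 45.
- P(X ≥ 9 | 45, 0.25) = 0.827, which agrees with the stated 82%.

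**3. Sensitivity to artefactual responses.** The documents give no rate, so both k and m below are assumptions. If k patients who would not otherwise respond are scored as responders and the remaining 45 − k respond at 10%, the chance of a positive test is P(X ≥ 9 − k | 45 − k, 0.10).

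| k | Chance of a positive ORR test at a true 10% rate |
|---|---|
| 0 | 3.2% |
| 1 | 6.8% |
| 2 | 13.3% |

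If instead a share m of non-responders is misclassified, the apparent rate is 0.10 + 0.90m:

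| m | Apparent rate | Chance of a positive ORR test |
|---|---|---|
| 1% | 10.9% | 5.1% |
| 2% | 11.8% | 7.7% |
| 5% | 14.5% | 19.7% |

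**4. How large a change is needed?** Response requires a 30% fall. That is 3 mm for a 10 mm lesion; for RECIST sums of 20, 50 and 100 mm it is 6, 15 and 30 mm. Only the smallest lesions or sums lie within plausible reach of a biopsy effect.

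**5. Could punches alone produce a 30% fall?** Take a round 10 mm nodule (radius 5 mm) and 5 mm punches, in flat geometry without healing.

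- One punch removes a stretch of margin with a chord of at most 5 mm, an angle of 2 × arcsin(2.5/5) = 60°.
- Two punches remove at most 120°. Breaking every pair of opposite margin points needs 180°, so one pair survives and the longest diameter stays 10 mm, a fall of 0%.
- Four punches (two at each time point, all in the same nodule) remove at most 240° and leave at least 120° of margin. The longest diameter is then at least 2 × 5 × sin 60° = 8.66 mm, a fall of at most (10 − 8.66)/10 = 13.4%.

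Neither reaches 30%. The check does not cover elongated lesions or contraction on healing, for which the documents give no figures.

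**The case against.** A reader might infer that punching alone can turn a 10 mm nodule into a responder, because two 5 mm punches take 2 × π × 2.5² = 39.3 mm² of its π × 5² = 78.5 mm², half the area. The documents do not support this. RECIST and the abscopal definition both use diameter, and by diameter the round nodule falls short of 30%. Appendix H also reserves skin for patients with no other biopsy-accessible site and accepts less tissue than the goal. No passage says that the same lesion is sampled twice.

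A reader might also infer that ORR is biased upward. That is not established either. Swelling, bleeding, or a biopsy taken before the baseline scan can all work against response. Only the best-lesion abscopal rule has a built-in upward tilt.

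Further points against the concern have weight. The reproducibility clause lets a careful reader avoid a disturbed lesion. The step from 8 to 9 responses shows only that the test has a boundary, which any misread scan could cross. Abscopal response is exploratory and ORR is secondary. For 18-gauge cores and sums of 50 mm or more, biopsy alone is unlikely to decide a response.

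These points limit the size of the problem but do not close the gap. The reproducibility clause is discretionary and silent on biopsy. In a patient with a single measurable lesion there is no next largest lesion to choose.

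**Conclusion.** The concern holds as a gap in the lesion-selection rules. A lesion sampled for research may also be a RECIST target or the reported abscopal lesion, and in patients with few measurable lesions the target rule makes it so. Biopsy effects can then change measured size in either direction in extracranial ORR, the abscopal rate and, through the nadir, PFS.

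No rate can be derived from the documents. The effect is probably small and confined to small lesions or single-target patients. The figure of 6.8% against 3.2% is conditional: it assumes exactly one artefactual response in a patient who would otherwise not respond, at a true rate of 10%. It is not an estimate of the actual error rate. The sample size, cutoff and power in Section 13.6.1 are unaffected. This is a worthwhile, inexpensive improvement, not a flaw that invalidates the ORR test.

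**What to change.** Add to Section 11.2.2 and to the abscopal definition in Section 11.4.3:

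- At baseline, identify the lesion intended for research biopsy at baseline and cycle 2. Where another measurable lesion exists, record the biopsy lesion as non-target and make it ineligible as the abscopal lesion.
- Where it is the only measurable lesion, keep it as target, record the dates and order of biopsy and scan at baseline and cycle 2, and flag the patient.
- Do not drop a target lesion after baseline. Targets are fixed before the cycle 2 biopsy, and a later removal would be a post-baseline change to the endpoint. If a target is sampled after all, it stays a target and the patient is flagged.
- Do not require the baseline measurement to follow the biopsy. That could build swelling into the reference, and its resolution would then look like response.

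Add a biopsied-lesion identifier to the CRF. Repeat ORR and the abscopal rate without flagged patients as a sensitivity analysis. That set will be smaller than 45 if anyone is flagged, so report estimates with intervals and do not carry over the 9 of 45 cutoff.

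The cost is protocol wording, one CRF field for the lesion, a note of biopsy and scan dates for the few flagged patients, and one fewer target lesion in some patients.
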